6.2. Storage and handling of study vaccine

The study vaccine must be stored at the respective label storage temperature conditions in a safe and locked place. Access to the storage space should be limited to authorized study personnel. The storage conditions will be assessed during pre-study activities under the responsibility of the sponsor study contact. The storage temperature should be continuously monitored with calibrated (if not validated) temperature monitoring device(s) and recorded. Refer to the Module on Clinical Trial Supplies in the SPM for more details on storage of the study vaccine.

Temperature excursions must be reported in degree Celsius.

Any temperature excursion outside the range of 0.0 to +8.0°C (for +2 to +8°C/+36 to +46°F label storage condition) impacting investigational medicinal products (IMPs) must be reported in the appropriate (electronic) temperature excursion decision form ([e]TDF). The impacted IMPs must not be used and must be stored in quarantine at label temperature conditions until usage approval has been obtained from the sponsor.

In case of temperature excursion below +2.0°C down to 0.0°C impacting IMP(s) there is no need to report in (e)TDF, but adequate actions must be taken to restore the +2 to +8°C/+36 to +46°F label storage temperature conditions. The impacted IMP(s) may still be administered, but the site should avoid re-occurrence of such temperature excursion. Refer to the Module on Clinical Trial Supplies in the SPM for more details on actions to take.

Refer to the Module on Clinical Trial Supplies in the SPM for details and instructions on the temperature excursion reporting and usage decision process, packaging and accountability of the study vaccine.

6.3. Dosage and administration of study vaccines

The dosage and administration of study vaccines is given in [Table 14](#).

Table 14 Dosage and administration (Amended 06 September 2016)

Type of contact and timepoint	Volume to be administered	Study group	Treatment name	Route ¹	Site	Side
Visit 1 (Day 0), Visit 2 (Month 2), Visit 3 (Month 4)* Or Visit 1 (Day 0), Visit 2 (Month 1), Visit 3 (Month 2)**	0.5 ml	dTpa Group and Control Group	Infanrix hexa	IM	Thigh	Right
Visit 1 (Day 0), Visit 2 (Month 2), Visit 3 (Month 4)* Or Visit 1 (Day 0), Visit 2 (Month 2)† Or Visit 1 (Day 0), Visit 2 (Month 1), Visit 3 (Month 2)**	0.5 ml	dTpa Group and Control Group	Prevenar 13	IM	Thigh	Left
Visit 1 (Day 0), Visit 2 (Month 2)***	0.5 ml	dTpa Group and Control Group	Infanrix hexa	IM	Thigh	Right
Visit 1 (Day 0), Visit 2 (Month 2)***	0.5 ml	dTpa Group and Control Group	Prevenar 13	IM	Thigh	Left

¹Intramuscular (IM)

*For subjects vaccinated with *Infanrix hexa* at 2, 4 and 6 months of age

** For subjects vaccinated *Infanrix hexa* at 2, 3 and 4 months of age

*** **For subjects vaccinated with *Infanrix hexa* at 2 and 4 months of age or at 3 and 5 months of age. These subjects will receive *Prevenar 13* at the same vaccination schedule.**

† In some countries/regions **with an *Infanrix hexa* 3-dose schedule**, *Prevenar 13* is given as a 2-dose schedule at 2 and 4 months of age as a part of the routine immunisation programme.

6.4. Replacement of unusable vaccine doses

In addition to the vaccine doses provided for the planned number of subjects, at least 5% additional vaccine doses will be supplied to replace those that are unusable.

6.5. Contraindications to subsequent vaccination

The following events constitute absolute contraindications to further administration of *Infanrix hexa*. If any of these events occur during the study, the subject must not receive additional doses of vaccine but may continue other study procedures at the discretion of the investigator (see Section 8.4).

- Anaphylaxis following the administration of vaccine.
- Hypersensitivity reaction to any component of the vaccine(s) and any excipients in the formulation.

- Any condition that in the judgment of the investigator would make intramuscular injection unsafe.
- Contraindication to *Infanrix hexa*:
 - Encephalopathy defined as an acute, severe central nervous system disorder occurring within 7 days following vaccination and generally consisting of major alterations in consciousness, unresponsiveness, generalised or focal seizures that persist more than a few hours, with failure to recover within 24 hours.

The following events constitute contraindications to administration of *Infanrix hexa* at that point in time; if any of these events occur at the time scheduled for vaccination, the subject may be vaccinated at a later date, within the time window specified in the protocol (see [Table 6 to Table 9](#) as applicable), or the subject may be withdrawn at the discretion of the investigator (see Section 8.4). (*Amended 06 September 2016*)

- Acute disease and/or fever at the time of vaccination.
 - Fever is defined as temperature $\geq 37.5^{\circ}\text{C}/99.5^{\circ}\text{F}$ for oral, axillary or tympanic route, or $\geq 38.0^{\circ}\text{C}/100.4^{\circ}\text{F}$ for rectal route. The preferred route for recording temperature in this study will be rectal/axillary.
 - Subjects with a minor illness (such as mild diarrhoea, mild upper respiratory infection) without fever can be administered all vaccines.

6.6. Warnings and precautions

The information below presents, in addition to the contraindications in Section 6.5, warnings and precautions to administration of *Infanrix hexa*.

- As with other vaccines, administration of *Infanrix hexa* should be postponed in subjects suffering from acute severe febrile illness. The presence of a minor infection is not a contraindication.
- Vaccination should be preceded by a review of the medical history (especially with regard to previous vaccination and possible occurrence of undesirable events) and a clinical examination.
- If any of the following events are known to have occurred in temporal relation to receipt of pertussis-containing vaccine, the decision to give further doses of pertussis-containing vaccines should be carefully considered:
 - Temperature of $\geq 40.0^{\circ}\text{C}$ within 48 hours, not due to another identifiable cause.
 - Collapse or shock-like state (hypotonic-hyproresponsiveness episode) within 48 hours of vaccination.
 - Persistent, inconsolable crying lasting ≥ 3 hours, occurring within 48 hours of vaccination.
 - Convulsions with or without fever, occurring within 3 days of vaccination.

- As with all injectable vaccines, appropriate medical treatment and supervision should always be readily available in case of a rare anaphylactic event following the administration of the vaccine.
- *Infanrix hexa* should be administered with caution to subjects with thrombocytopenia or a bleeding disorder since bleeding may occur following an intramuscular administration to these subjects.
- In children with progressive neurological disorders, including infantile spasms, uncontrolled epilepsy or progressive encephalopathy, it is better to defer pertussis (Pa or Pw) immunisation until the condition is corrected or stable. However, the decision to give pertussis vaccine must be made on an individual basis after careful consideration of the risks and benefits.
- Do not administer the vaccine intravascularly or intradermally.
- The potential risk of apnoea and the need for respiratory monitoring for 48-72 hours should be considered when administering the primary immunisation series to very preterm infants (born ≤ 28 weeks of gestation) and particularly for those with a previous history of respiratory immaturity. As the benefit of vaccination is high in these infants, vaccination should not be withheld or delayed.
- A protective immune response may not be elicited in all vaccinees.
- A history of febrile convulsions, a family history of convulsions or Sudden Infant Death Syndrome (SIDS) do not constitute contraindications for the use of *Infanrix hexa*. Vaccinees with a history of febrile convulsions should be closely followed up as such adverse events may occur within 2 to 3 days post vaccination.
- Since the Hib capsular polysaccharide antigen is excreted in the urine, a positive urine test can be observed within 1-2 weeks following vaccination. Other tests should be performed in order to confirm Hib infection during this period.
- Data from clinical studies indicate that, when *Infanrix hexa* is co-administered with pneumococcal conjugate vaccine, the rate of febrile reactions is higher compared to that occurring following the administration of *Infanrix hexa* alone.
- Increased reporting rates of convulsions (with or without fever) and hypotonic hyporesponsive episode (HHE) were observed with concomitant administration of *Infanrix hexa* and *Prevenar 13*.

Refer to the approved product label/package insert for warnings and precautions for the use of *Prevenar 13*.

6.7. Concomitant medications/products and concomitant vaccinations

At each study visit, the investigator should question the subject's parent(s)/LAR(s) about any medications/products taken and vaccinations received by the subject.

6.7.1. Recording of concomitant medications/products and concomitant vaccinations

The following concomitant medications/products/vaccines must be recorded in the eCRF.

- All concomitant medications/products, except vitamins and dietary supplements, administered in the period starting from the first dose of study vaccines (Visit 1) and ending at the last study visit (Visit 4).
- Any concomitant vaccination administered in the period starting from the administration of the first dose of study vaccines (Visit 1) and ending at the last study visit (Visit 4). Note: Medications/vaccinations listed prior to the first dose of study vaccines are to be recorded as medical/vaccination history.
- Prophylactic medication (i.e. medication administered in the absence of ANY symptom and in anticipation of a reaction to the vaccination).
E.g. an anti-pyretic is considered to be prophylactic when it is given in the absence of fever and any other symptom, to prevent fever from occurring [fever is defined as temperature $\geq 37.5^{\circ}\text{C}/99.5^{\circ}\text{F}$ for oral, axillary or tympanic route, or $\geq 38.0^{\circ}\text{C}/100.4^{\circ}\text{F}$ for rectal route].
- Any concomitant medications/products/vaccines listed in Section 6.7.2.
- Any concomitant medications/products/vaccines relevant to a SAE to be reported as per protocol or administered at any time during the study period for the treatment of a SAE. In addition, concomitant medications relevant to SAEs need to be recorded on the expedited Adverse Event report.

6.7.2. Concomitant medications/products/vaccines that may lead to the elimination of a subject from ATP analyses

The use of the following concomitant medications/products/vaccines will not require withdrawal of the subject from the study but may determine a subject's evaluability in the ATP analysis. See Section 10.4 for cohorts to be analysed.

- Any investigational or non-registered product (drug or vaccine) other than the study vaccines used within 30 days preceding the first dose of study vaccines, or planned use during the study period.
- Immunosuppressants or other immune-modifying drugs administered chronically (i.e. more than 14 days) since birth. For corticosteroids, this will mean prednisone ≥ 0.5 mg/kg/day, or equivalent. Inhaled and topical steroids are allowed.
- Long-acting immune-modifying drugs administered at any time during the study period (e.g. infliximab).
- A vaccine not foreseen by the study protocol administered during the period starting from 30 days before each dose of vaccine and ending 30 days after*, with the exception of inactivated influenza vaccine and other vaccines given as a part of the

national/regional immunisation schedule, that are allowed at any time during the study period.

In case an emergency mass vaccination for an unforeseen public health threat (e.g.: a pandemic) is organised by the public health authorities, outside the routine immunisation programme, the time period described above can be reduced if necessary for that vaccine provided it is licensed and used according to its SmPC or Prescribing Information and according to the local governmental recommendations and provided a written approval of the Sponsor is obtained.

- Immunoglobulins and/or any blood products administered during the study period.

6.8. Intercurrent medical conditions that may lead to elimination of a subject from ATP analyses

At each study visit subsequent to the first vaccination, it must be verified if the subject has experienced or is experiencing any intercurrent medical condition. If it is the case, the condition(s) must be recorded in the eCRF.

Subjects may be eliminated from the ATP cohort for immunogenicity if, during the study, they incur a condition that has the capability of altering their immune response (e.g. any confirmed or suspected immunosuppressive or immunodeficient condition) or are confirmed to have an alteration of their initial immune status.

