* History of all medications given to the infants will be recorded in the eCRF.

** Subject receiving 2 doses of Infanrix hexa will not attend the Visit 3

The intervals between study visits for subjects *receiving 3 doses of Infanrix hexa* at 2, 4 and 6 months and 2, 3 and 4 months are presented in [Table 6](#) and [Table 7](#), respectively. *The intervals between study visits for subjects receiving 2 doses of Infanrix hexa at 2*

and 4 months and at 3 and 5 months are presented in [Table 8](#) and [Table 9](#), respectively. (Amended 06 September 2016)

Table 6 Intervals between study visits for subjects vaccinated with *Infanrix hexa* at 2, 4 and 6 months of age (Amended 06 September 2016)

Interval	Optimal length of interval ¹	Allowed interval ^{2†}
Birth →Visit 1	60 days	42-104 days
Visit 1→Visit 2	60 days	52 - 78 days
Visit 2→Visit 3	60 days	52 - 78 days
Visit 3→Visit 4	30 days *	21 -48 days

¹. Whenever possible the investigator should arrange study visits within this interval.

². Subjects will not be eligible for inclusion in the ATP cohort for analysis of immunogenicity if they make the study visit outside this interval.

† Date of previous visit/contact is the reference date

*If subjects return for the visits prior to 30 days, the parent(s)/LAR(s) should take home the diary card and continue to record unsolicited safety information until 30 days post-vaccination and mail/send it upon completion. Investigators will make an attempt to retrieve diary cards from subjects' parent(s)/LAR(s) who have not mailed/sent them in.

Table 7 Intervals between study visits for subjects vaccinated with *Infanrix hexa* at 2, 3 and 4 months of age (Amended 06 September 2016)

Interval	Optimal length of interval ¹	Allowed interval ^{2†}
Birth→Visit 1	60 days	42-104 days
Visit 1→Visit 2	30 days	21 -48 days
Visit 2→Visit 3	30 days	21 -48 days
Visit 3→Visit 4	30 days *	21 -48 days

¹. Whenever possible the investigator should arrange study visits within this interval.

². Subjects will not be eligible for inclusion in the ATP cohort for analysis of immunogenicity if they make the study visit outside this interval.

† Date of previous visit/contact is the reference date

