2080	
Vaccination done but: noncompliance with vaccination schedules (dates of vaccination not corresponding to protocol intervals or unknown vaccination dates)
 
Intervals between study visits for subjects vaccinated with Infanrix hexa at 2, 4 and 6 months of age is 42-104 days from birth to visit 1, 52-78 days from visit 1 to visit 2, 52-78 days from visit 2 to visit 3.
 
Intervals between study visits for subjects vaccinated with Infanrix hexa at 2, 3 and 4 months of age is 42-104 days from birth to visit 1, 21-48 days from visit 1 to visit 2, 21-48 days from visit 2 to visit 3.
 
Intervals between study visits for subjects vaccinated with Infanrix hexa at 2 and 4 months of age is 42 to 104 days from birth to visit 1, 52-78 days from visit 1 to visit 2.
 
Intervals between study visits for subjects vaccinated with Infanrix hexa at 3 and 5 months of age is 42 to 104 days from birth to visit 1, 52-78 days from visit 1 to visit 2.

2090	
Blood sample taken but: noncompliance with blood sampling schedules (dates of blood sampling not corresponding to adapted protocol intervals or unknown blood sample/vaccination dates) => 21-48 days from last vaccination visit to visit 4

2100	
Serological results not available for antigens POST vaccination (including lost samples, blood sample not done, unable to test, absence of parallelism) => no immunogenicity results available at visit 4.

2120	
Obvious incoherence, abnormal serology evolution or error in data (incoherence between CRF and results, wrong sample labelling)

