- The verbatim reports of unsolicited AEs will be reviewed by a physician and the signs and symptoms will be coded according to MedDRA. Every verbatim term will be matched with the appropriate Preferred Term. The percentage of subjects with unsolicited AEs occurring within 31-day (Day 0- Day 30) follow-up period after any dose with its exact 95% CI [Clopper, 1934] will be tabulated by group, and by preferred term. Similar tabulation will be done for unsolicited AEs rated as grade 3, for unsolicited AEs with causal relationship to vaccination and AEs/SAEs leading to withdrawal from the study.
- The percentage of subjects who receive concomitant medication and antipyretic medication during the 4-day (Day 0- Day 3) follow-up period and the 31-day follow-up (Day 0 – Day 30) will be tabulated (with exact 95% CI [Clopper, 1934]) after each vaccine dose and overall.
- SAEs reported from first vaccination dose up to study end will be described in detail.
- Withdrawal due to AEs and SAEs following vaccinations will be described in detail.

Handling of missing data:

- For a given subject and the analysis of solicited AEs 4 days post-vaccination, missing or non-evaluable measurements will not be replaced. Therefore, the analysis of the solicited AEs based on the TVC will include only vaccinated subjects and doses with documented safety data (i.e. symptom screen completed).
- For analysis of unsolicited AEs, such as SAEs or AEs by primary Medical Dictionary for Regulatory Activities (MedDRA) term, and for the analysis of concomitant medications, all vaccinated subjects will be considered. Subjects, who do not report the event or the concomitant medication, will be considered as subjects without the event or the concomitant medication, respectively.
- For summaries reporting both solicited and unsolicited AEs, all vaccinated subjects will be considered. Subjects, who do not report the event or the concomitant medication, will be considered as subjects without the event or the concomitant medication, respectively.

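### Concomitant medication is recorded only to Visit 4, which may precede Day 30, yet is tabulated for Day 0-30 with no report counted as no use, so 31-day last-dose and overall percentages can only err low

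*Protocol*

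**What the plan says.** **Recording.** Protocol Section 6.7.1 leaves out vitamins and supplements and otherwise covers any concomitant medication "administered in the period starting from the first dose of study vaccines (Visit 1) and ending at the last study visit (Visit 4"). A parallel bullet sets the same limits for concomitant vaccination. Section 6.7 gives the method: "At each study visit, the investigator should question the subject's parent(s)/LAR(s) about any medications/products taken". The visible text lists no contact after Visit 4.

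**Timing of Visit 4.** Protocol Tables 6-9 set an optimal interval of 30 days after the last dose on every schedule. SAP Section 5.2.3.1 (code 2090) repeats the allowed range: "21-48 days from last vaccination visit to visit 4".

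**Early visits.** Under the footnotes to Tables 6-9, parents of an infant seen before Day 30 take the diary card home and "continue to record unsolicited safety information until 30 days post-vaccination and mail/send it upon completion". Medication is not named.

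**Analysis.** Under SAP Section 6.4.1, the percentage with any and with antipyretic medication in the 4-day period and "the 31-day follow-up (Day 0 – Day 30) will be tabulated", after each dose and overall. The missing-data rule uses all vaccinated subjects and adds: "Subjects, who do not report the event or the concomitant medication, will be considered as subjects without the event or the concomitant medication, respectively". SAP Section 11.2.5 repeats both the rule and the denominator. No adjustment for a shortened window is stated.

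**The concern.** The recording period and the analysis window end at different times. For an infant whose Visit 4 falls on Days 21-29, the days from then to Day 30 lie outside the stated recording period. The SAP nevertheless analyses them as days without medication. That error runs in one direction only: it can turn a user into a non-user, never the reverse.

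At stake is the descriptive 31-day medication summary, in its last-dose and overall rows. A reader who uses it to judge antipyretic or other medication use after vaccination would see figures that are too low by an unstated amount. On schedules with at least 52 days between doses, earlier doses have their full 31 days covered and the last dose may not. Comparing doses there partly reflects visit timing.

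**Working it through.** The plan states no expected medication rate or visit-timing distribution, so it has no figure to reproduce. The check is a count of days, followed by an illustration on assumed inputs.

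**1. Days outside the recording period.** Day 0-30 has 31 days. If Visit 4 is on Day v, with v at most 30, the unrecorded days number 30 − v.

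| Visit 4 | Unrecorded days | Share of 31 |
|---|---|---|
| Day 21 | 9 | 29.0% |
| Day 24 | 6 | 19.4% |
| Day 28 | 2 | 6.5% |
| Day 29 | 1 | 3.2% |
| Day 30 or later | 0 | 0% |

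A visit before Day 21 would lose more. Such an infant leaves the ATP immunogenicity cohort but stays in the total vaccinated cohort, on which the primary safety analysis is based.

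**2. Effect on the last-dose percentage.** The summary counts subjects with at least one use. Let P be the true 31-day percentage and assume a constant start rate. Then recorded % = 1 − (1 − P)^((v+1)/31). For P = 40% and v = 21, this is 1 − 0.6^(22/31) = 30.4%, or 9.6 points low. The shortfall scales with the share of infants seen that early. P and that share are both assumptions.

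| True P | All on Day 21 (extreme of window) | 30% on Day 21 | 30% on Day 28 |
|---|---|---|---|
| 20% | −5.4 points | −1.6 | −0.3 |
| 40% | −9.6 | −2.9 | −0.6 |
| 60% | −12.2 | −3.7 | −0.7 |

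If use clusters early the loss shrinks. Suppose 50-75% of users start on Days 0-3 and the rest start evenly over the 27 days from Day 4 to Day 30. A Day 21 visit then loses (1 − s) × 9/27 of users, where s is the early share. A true 40% is recorded as 33.3-36.7%.

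**3. Overall rows.** With k doses, independent use at each dose and every Visit 4 on Day 21, the true percentage per subject is 1 − (1 − P)^k. The recorded percentage is 1 − (1 − P)^(k−1) × (1 − recorded last-dose %). For P = 40% and k = 3 this gives 78.4% against 74.9%, or 3.5 points low. Over P = 20-60%, the per-subject shortfall is 2.0-3.5 points for three doses and 4.3-5.8 for two. The per-dose shortfall is the last-dose shortfall divided by k: 1.8-4.1 points for three doses and 2.7-6.1 for two. These too are extremes.

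**4. Which schedules show the asymmetry between doses.** SAP Section 11.2.2 assigns a medication to the most recent dose. On the 2,4,6, 2,4 and 3,5 schedules, the minimum interval between doses is 52 days, so earlier doses have a full window. These schedules hold 457 + 7 + 66 = 530 of the 601 infants tabulated in SAP Section 6.3.2. On the 2,3,4 schedule (71 infants), Table 7 also allows 21 days between doses, so earlier-dose windows can be cut at Day 21 as well. There, however, later use is still recorded and assigned to the next dose.

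**The case against.** The strongest objection is that the diary card may collect medication to Day 30 anyway. Most of Sections 5.6.12 to 5.6.14 was not in the copy of the protocol used here, so a medication entry on the take-home card cannot be excluded. A reader might infer that post-Visit 4 use is established as unobserved and the percentages as biased. The documents do not support that; they support a mismatch between the stated rules. Tables 4 and 5 do not settle it. Their medication row ends at Visit 4, but so does the non-serious adverse event row, and those events are collected to Day 30.

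Section 8.5 asks for medication given to treat an adverse event to be entered in the eCRF, and Section 6.7.1 has its own bullet for medication linked to serious events. An antipyretic first given on Days 22-30 would often accompany a recorded event. Prophylactic use in anticipation of a vaccine reaction is unlikely that late. This narrows the loss but does not close it. Section 8.5 refers back to Section 6.7, and medication not tied to an event has no stated route after Visit 4.

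Three stronger readings also fail:

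- **A known size.** If 20-40% of infants attended evenly over Days 21-29, the mean loss would be 5 of 31 days (16%), so 3-6% of last-dose starts would be missed. That counts starts on assumed attendance. The summary counts subjects, and an infant already counted earlier in the window loses nothing.
- **A difference between groups.** Both groups follow the same rule, and nothing indicates different Visit 4 timing.
- **An asymmetry between doses on every schedule.** It does not hold for 2,3,4.

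**Conclusion.** The mismatch stands. Taken as written, Section 6.7.1, the Visit 4 window, the diary footnote and the no-report rule can only understate 31-day medication use after the last dose and overall. They do so only for infants seen before Day 30. Up to 9 of 31 days are unrecorded within the allowed window.

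The effect on the percentages is unknown and probably small. The visit target is 30 days, some use may be recovered through Section 8.5, and early clustering of use would reduce it further. The point counts in the illustration depend on assumed use, visit timing and start pattern.

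The consequence is limited. The summary is descriptive, and no primary or secondary endpoint in Protocol Sections 10.1 and 10.2 uses medication. The Day 0-3 medication table (SAP Template 23) is untouched. This is a minor alignment of collection and analysis.

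**What to change.** **Protocol.** In Section 6.7.1, end the recording period for medication and vaccination at Visit 4 or Day 30 after the last dose, whichever is later. In the footnotes to Tables 6-9, add medication and vaccination to what parents record on the take-home card. This brings the unrecorded days to zero, provided the cards are returned. It costs slightly more transcription for infants seen before Day 30. If the card already collects medication to Day 30, saying so in Section 6.7.1 is enough.

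**SAP, if data are already collected.** The SAP of 16 July 2018 already tabulates 601 infants, so this may be the practical route. If the card did not capture medication after Visit 4, either:

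- base the last-dose 31-day percentage on infants observed to Day 30, and flag or treat the overall rows likewise. This removes the shortfall at the cost of a slightly smaller denominator, and assumes that infants seen early are similar to the rest; or
- label the window as ending at the earlier of Day 30 and Visit 4. If nothing was recorded after Visit 4 this changes no count, so it describes the shortfall correctly without removing it.

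In either case, report by group the number of infants with fewer than 31 days observed after the last dose.
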